#### STUDY FLOW: bе-**Identification and Screening** Follow-up Allocation COMMUNITY RECRUITMENT SOURCE **Attention Control** VISIT 2: 1.Confirm blood pressure eligibility VISIT 6 (12M): 2.Confirm medications VISIT 4 (4M): VISIT 5 (6M): VISIT 3 (2M): Surveys sent 1 week 3. Randomize ASA-24 2 sent weeks Surveys sent 1 week ASA-24 2 sent weeks SCREENING/CONSENT prior: ASA-24 2 sent 4. Show welcome video prior prior: ASA-24 2 sent prior 1. Online screener weeks prior for appropriate study 1. Take BP weeks prior 1. Take BP 2. E-consent 1. Take BP 2. ASA24 if not 1. Take BP 2. ASA24 if not 3. Online survey "Getting to 2. ASA24 if not 5. Schedule Visit 3 complete 2. ASA24/6-month complete know you" measures complete 3. Confirm survey, if not complete 3.Confirm medications 3. Confirm Intervention arm only: medications 3. Confirm medications 4. Schedule Visit 4 medications Personalization survey 4. Schedule Visit 5 4. Schedule Visit 6 4. Final survey and schedule coach onboarding call -ASA-24 emails (for weekday and weekend After Visit 5: recall) 9-month retention Satisfaction survey -Schedule Visit 1 protocol/shipment emailed -PH app download 7-day dietary tracking run-in instructions with appt period in app. confirmation Fed Ex box of materials. including BP monitor, after 4 days of consecutive tracking Intervention VISIT 1: VISIT 5 (6M): VISIT 6 (12M): VISIT 3 (2M): VISIT 4 (4M): 1. Overview of 7-day dietary ASA-24 2 sent weeks ASA-24 2 sent weeks Survevs sent 1 week Surveys sent 1 week tracking prior prior prior: ASA-24 2 sent prior: ASA-24 2 sent 2. Tracking app weeks prior 1. Take BP 1. Take BP weeks prior download/registration. if 2. ASA24 if not complete 1. Take BP 1. Take BP 2. ASA24, if not needed 3.Confirm medications 2. ASA24 if not complete 2. ASA24/6-month 3. Show BP video 4. Confirm survey, if not complete complete 3. Confirm medications 4. Confirm shipping address 4. Confirm personalization survey 3. Confirm medications 3. Confirm 5. (Tentatively) Schedule Visit 2 medications personalization survey 5. Schedule Visit 5 4. Schedule Visit 6 5. Schedule Visit 4 4. Final survey After Visit 5: 9-month retention Satisfaction survey protocol/shipment emailed

# Nourish measures/constructs

	Online	Online survey	Visit 1: Dietary	Visit 2: Randomization occurs	Follow-up visits (by month)			
Construct or Measure	eligibility screener ("Getting to Know you")		tracking confirmation/ orientation		Visit 3: (2 Mo)	Visit 4: (4 Mo)	Visit 5: (6 Mo)	Visit 6: (12 Mo)
Dietary Intake		,						
• ASA-24*			x*		х	х	X	х

 
Food allergies/restrictions (5-items)
 
		х						
Blood pressure						•		•
Hypertension screener	х							
Blood pressure (Zoom call-verified)				х	х	х	Х	х
Blood pressure tendency to run high		х						
Blood pressure home self-monitoring		х					х	х
Anthropometrics						,		
Self-reported Weight	х							
Self-reported Height	х							
Medication use						,		

 
Current blood pressure meds/dosage**
 
		х		х	х	х	Х	Х
Voils blood pressure med adherence (3		х					х	х
items)^								
Smoking								
HINTS smoking questions (3 items)		х					X	х
Physical activity:								
NPAQ		х					X	х
Self-efficacy for healthy eating:						,		
Nutrition Self Efficacy Scale		х					Х	Х
Intuitive Eating Scale-2 (IES-2)		х					Х	Х

Psychosocial:								
• Stress		х					х	х
• Sleep		х					х	х
• PHQ-8		х					х	х
Every day discrimination		х						
Experiences of discrimination		х						
Technology use:								
Smartphone type		X						
Cell phone usage frequency		х						
Text messaging frequency		х						
Unlimited texting plan		х						

 
Internet access and usage (3 items)
 
		x						
Time owning a smartphone		x						
Smartphone App usage (4 items)		х						
Demographics:				,				
Gender (2-items)	χ^^	X^^						
Age (from DOB at PH app registration)			х					
Age (self-reported on survey)		х						
Race/ethnicity		x						
Education		х						
Household income		х						
Employment (3 items)		х						
Marital status		x						
Household composition (4-items)		х						
Home ownership		х						
Car ownership		x						
Public assistance (2-items)		Х						

Insurance status	Х				
Personalization survey (Ix arm only)		х	Х	Х	

x\* ASA 24 collection occurs during 2-week period prior to visits (Visit 1, Follow-up visits Visit 3-6). After Visit 1, if participant tracks for 4 consecutive days on the Pattern Health app, will receive a box with materials. If eligible in BP range, will be randomized at Visit 2.

x\*\* Medications are asked on the screener (if taking BP meds) but specifics/dosages are on the pre-visit surveys and confirmed during the visits

x^ Voils et al's 3-item adherence

x^^ Gender on the screener asks about sex at birth, self-identified gender asked on online evaluation survey

#### **Descriptions:**

Current medication use will be assessed using a similar protocol from Voils et al.

Physical activity: Nordic Physical Activity Questionnaire-short form (NPAQ)

Engagement with the intervention will be measured as the proportion of days tracked over expected, DASH nutrient adherence, and number/proportion of coaching encounters attended over the number expected in each zone.

Self-efficacy for healthy eating will be measured using the Nutrition Self Efficacy Scale and Intuitive Eating Scale- 2 (IES-2)

Depression will be measured using the Patient Health Questionnaire (PHQ-8); a validated measure for assessing depressive symptoms in community populations.

Sociodemographics include measures such as race/ethnicity, health insurance, income, employment status, education, household size, technology use, etc.

[REDCap eligibility screening landing page]

# Welcome and thank you for your interest in the Nourish study!

#### What is Nourish?

Nourish is a research study that investigators at Duke University are doing to help adults with high blood pressure follow an eating pattern that can lower blood pressure and improve health.

#### What's involved?

If you join Nourish, you will be asked to track what you eat and drink every day through a smartphone app and to participate in study visits over one year. You will receive information on how to improve your eating habits using the DASH (Dietary Approaches to Stop Hypertension) eating pattern. You will be compensated for your time, starting at the second visit.

# How do I participate?

To see if this study is right for you and if you are eligible, click "Next" below and answer a few questions. If you are eligible for the study, we'll give you some more information before you decide if you would like to join.

# **Screening Survey**

At the bottom of each screening question page below, there is a footer that says: Questions? Contact us at [contact] or [contact]

Question	Options	Skip logic	Exclusion rules
1. How did you hear about this study?	FacebookClinical trials website (Clinicaltrials.gov)Researchmatch.orgDuke MyChart messageCommunity forum or listserv (e.g. Nextdoor)CraigslistCommunity organization post/emailDuke website or listingTwitterRedditSomeone told me about itDon't knowOther:  1a. Please describe how you heard about the study:	If "Other" is selected, go to 1a Otherwise skip to 2	
2a. Have you ever been told by a doctor or other health professional that you have high blood pressure, also called hypertension?	Yes No Not sure/I don't know	All responses – ask 2b	Exclude if answer No to ALL 2 (2a, 2b, 2c AND 2d) If answer yes to any of them, still eligible.
2b. Are you currently taking medication to control your blood pressure?	Yes No	If yes to 2a OR 2b, skip to 3	

(Include any medication meant to help control your blood pressure, including diuretics or "water pills.		If no/don't know, ask 2c	
If no or Not sure/I don't know to question 2a AND No to 2b ask 2c:  2c. Think about the last time you got your blood pressure tested. Was the top number, also known as systolic blood pressure, in this range: 120-159?	Yes No I don't know/I don't remember	If yes to 2c, skip to 3  If no or I don't know/I don't remember, ask 2d	
If no or I don't know/I don't remember to question 2c:  2d. Think about the last time you got your blood pressure tested. Was the bottom number, also known as diastolic blood pressure, in this range: 80-99?	Yes No I don't know/I don't remember		
3. Do you have a smartphone with a data plan?	Yes No		Exclude if no

 
If needed, would you be willing to update your smartphone operating system to the most recent version?
 
(For example, this might mean changing your operating system from version 10 to version 10.1. We are not asking you to update your actual smartphone/device).
 
	Yes No		Exclude if no
5. To participate in Nourish remotely, you will need to complete at least 6 visits with our research team on a videoconference platform, such as Zoom. Are you willing and able to do this?	Yes No		Exclude if no
6. Do you have an email address?	Yes No		Exclude if no

7. Are you able to write and speak English fluently?	Yes No		Exclude if no
8. Are you currently 18 years old or older?	Yes, I'm 18 or older No, I'm younger than 18		Exclude if no
9. What was your sex assigned at birth?	Male Female	If male, skip to 10 If female, continue to 9a	
9a. If female ask: Are you pregnant or planning to become pregnant in the next 12 months?	Yes No	Continue to 10.	Exclude if yes
10. Have you ever been told by a doctor or other health professional that you had a heart attack, also called a myocardial infarction?	Yes No	If No, skip to 11 If Yes, continue to 10a	
10a. If yes, was it in the last 6 months?	Yes No		Exclude if yes
11. Have you ever been told by a doctor or other health professional or a stroke, also called an ischemic attack?			Exclude if yes
11a. If yes, was it in the last 6 months?	Yes No		
12. Do you have cancer?	Yes No	If No, skip to 13 If Yes, continue to 12a	
12a. If yes, is it in remission?	Yes No		Exclude if no
13. Have you had bariatric surgery (also called weight loss surgery) in the last 12 months or are you planning on having bariatric surgery in the next 12 months?	Yes, had surgery in the last 12 months Yes, planning on surgery in the next 12 months No		Exclude if yes (past or planned bariatric surgery)
14. Are you on dialysis?	Yes No		Exclude if yes
15. Have you been told by a healthcare provider to lower the amount of potassium you eat?	Yes No		Exclude if yes

16. Have you ever been hospitalized for a psychiatric condition or event?	Yes No	If No, skip to 17 If Yes, continue to 16a	
16a. If yes, was it in the last 6-months?	Yes No		Exclude if yes
17. Have you been diagnosed with dementia?	Yes No		Exclude if yes
18. What is your height?	feet inches		Calculate BMI = 703 × weight (lbs) / [height (in)] 
19. What is your current weight?	pounds		and exclude if less than 18.5
20. Are you currently participating in another study or clinical trial to change what you eat, your blood pressure or overall heart health?	Yes No		Exclude if yes
This includes drug trials as well as studies to help you improve your health habits or behaviors.			
21. Do you know anyone else participating in the Nourish study?	Yes No		If Yes, ask Question 21a. If No go to 22.
21a. Does the person participating in the Nourish study live with you?	Yes No		If yes to Question 21 and yes 21a, exclude
22. Do you currently live in the United States?	Yes No		If yes, go to end of screener. If No exclude.

At the end of the screener, after they answer all the questions, score the questions such that they are excluded if they answer any question as indicated by the last column in the table above.

\* For all ineligible participants web page will state:

Thank you for your interest in the Nourish study and for taking the time to answer these questions. Unfortunately, based on your responses, you are not eligible to join Nourish at this time.

If you would like us to keep your information on-file for any future studies we may have, please email us at [contact].

\*\*For all eligible participants web page will state:

[Thank you for answering our survey. Based on your responses, this study might be right for you.

Please press "Submit" to watch a short video about what Nourish is all about. After the video, you will have the chance to learn more about the study and your part in it, so you can decide if you want to participate. We will ask you to review and sign a form that lists out all the risks and benefits of Nourish study activities.

You can contact us with questions at [contact] or [contact] or sign the form if you are ready to participate.]

After REDCap e-consent form signed, participant will receive an emailed copy with this information:

[Welcome to Nourish! First, we'll need some more information about how we can reach you and where we can send our study materials to you]

[Collect phone numbers, mailing address to ship study materials]

[Over the next month, we will need to schedule 2 online meetings with you. We will contact you to make these appointments when we get to that step, but it will help us to know some days and times when you generally might be available]

Nourish: Using digital health to improve diet quality among adults at risk for cardiovascular disease (NCT03875768)
[List of days/times with checkboxes]
"Getting to know you" Survey (BASELINE SURVEY)
[Thank you. We will reach out to schedule your first appointment after you complete your surveys.]
The survey questions we are about to ask you will help us find out more about people who join the Nourish Study.

 
There are no "right" or "wrong" answers to any of these questions.
 
This survey should take 30-45 minutes to complete.
 
All aspects of the study are voluntary and you can quit at any time.
 
This survey must be completed before the next step of the study.
 
If you can't finish all at once, you can stop and start again at any time by clicking the Save & Return Later button below.]
 

We'd like to know about how you use technology in your daily life.

 
1. What kind of smartphone do you have?
 
 Apple iPhone
 
 Android (Google)
 
 Windows Phone
 
 Something else
 

2. How often do you use your cell phone? Often Sometimes Rarely

3. How often do you send text messages?

33

N	Jourish: Using digital health to improve diet quality among adults at risk for cardiovascular disease (NCT03875768)
-	OftenSometimesRarely
4. - -	Do you have an unlimited texting plan? Yes No Don't know
5.	Do you currently subscribe to internet service at home? This does not include your data plan for your smartphone.  Yes No
	Don't know
6.	If "No", Please tell me whether any of the following are reasons why you do not have high-speed internet at home.  The monthly cost of a home broadband subscription is too expensive  The cost of a computer is too expensive  Your smartphone lets you do everything online that you need to do  You have other options for internet access outside of your home  Broadband service is not available where you live, or is not available at an acceptable speed  Some other reason
7.	How do you access the internet most frequently?
	Cell phone Desktop/laptop Tablet

8. Over how many months or years have you had a smartphone? < 6 months 6-11 months 1-2 years More than 2 years Not sure 9. Do you use apps? Yes No If yes, they do you use apps: 10. On a scale of 0-10, with 0 being "Not at all comfortable" and 10 being "very comfortable," how comfortable are you using applications ("apps") on your smartphone? (0-10)If yes, they do you use apps: 11. Have you ever used an app to track the following? (Select all that apply) Blood pressure Weight Physical activity Diet Medication None of these If yes, they do you use apps: 12. Have you ever used an electronic or wearable device to track the following? (Select all that apply) **Blood** pressure Weight Physical activity

Nourish: Using digital health to improve diet quality among adults at risk for cardiovascular disease (NCT03875768)

Nourish: Using digital health to improve diet quality among adults at risk for cardiovascular disease (NCT03875768	3)
Diet	
Medication	
None of these	
Now, we'd like to ask you about your demographic information.	
13. What is your current age?	
years	
14a. How would you describe your gender?	
Male	
Female	
Prefer to self-describe	
Prefer not to say	
12b.If "prefer to self-describe" is selected:	
How would you describe your gender?	
14. Do you identify as transgender?	
Yes	
No	
Prefer not to say	
15. Do you consider yourself to be Hispanic or Latino? Yes, Hispanic or Latino	
No, not Hispanic or Latino	
Prefer not to say	
16. What race do you consider yourself to be? Please mark all the categories that you identify with American Indian or Native American	

Nourish: Using digital health to improve diet quality among adults at risk for cardiovascular disease (NCT03875768)
Asian
Native Hawaiian or Pacific Islander
Black or African American
White
Another race
Prefer not to say
17. If "another race" is selected: "Which other race?:
18. What is the highest level of schooling you completed?
Never attended school or only attended kindergarten
Grades 1 through 8 (Elementary school)
Grades 9 through 11 (Some high school)
Vocational or trade school after high school
Some college or university
Associate degree from college or university
College, 4 years or more (College graduate)
Post-graduate degree
19. Which of these categories best describes your total combined household income for the past 12 months? This should include gross income (before taxes) from all sources, wages, rent from properties, social security, disability, and/or veteran's benefits, unemployment benefits,
workman's compensation, help from relatives (including child payments and alimony) and so on.
Less than \$5,000
\$5,000 through \$11,999
\$12,000 through \$15,999
\$16,000 through \$24,999
\$25,000 through \$34,999
\$35,000 through \$49,999
\$50,000 through \$74,999
\$75,000 through \$99,999
\$100,000 or greater
Don't know

20. Which of the following best describes your current main daily activities and/or responsibilities? Select all that apply. Working full time \_\_ Working part-time Student Unemployed or laid off Looking for work Keeping house or raising children full-time Retired 21. (If answer unemployed or laid off, or looking for work) How long have you been out of work? Please enter number of week or months Weeks Months 22. (if answer working full time or working part-time) Are you satisfied with the number of hours you are working? \_\_\_\_ No, too few hours No, too many hours 23. Are you currently living with a spouse or partner? No 24. a. How many people are currently living in your household, including yourself? Number of people b. Of these people, how many are children 18 years or younger? Number of children c. Of these people, how many are adults, including yourself?

Nourish	: Using digital health to improve diet quality among adults at risk for cardiovascular disease (NCT03875768)
d. O	Number of adults f the adults, how many bring income into the household? Number of adults
25. Is the	home where you live:
	Owned by you or someone in the household with a mortgage or loan? Include home equity loans.
	Owned by you or someone in the household free and clear (without a mortgage or loan)?
	Rented?
	Occupied without payment of rent?
	Other, please specify:
26. Do yo	ou own a car?
Ye	S
No	
27. Has y	our family received any support from the SNAP Program (food stamps)?
Y	es
N	o .
28. Has y	our family received any support from the Special Supplemental Nutrition Program for Women, Infants and Children (WIC)?
Y	es
N	0
29. What	type of health insurance do you have?
	rivate insurance (such as Blue Cross Blue Shield, CIGNA, Health America, Aetna)
N	
	edicare
N	one, I pay out of pocket
(	ther please specify:

Nourish: Using digital health to improve diet quality among adults at risk for cardiovascular disease (NCT03875768)
30. Does your blood pressure tend to run high?  Yes  No
NO
31. Have you ever had a blood pressure reading where the systolic blood pressure (the top number) was over 160, or the diastolic blood pressur (the bottom number) was over 100?  Yes
No
32. Do you ever measure your blood pressure outside of appointments with your health care provider?  Yes No
If Yes ask next 3 questions:
33. Where do you measure your blood pressure? (select all that apply)
At home
At a pharmacy
At a friend or relative's house
At a community fair or event Other, please specify:
34. How often do you measure your blood pressure in any of these places?
3 or more times per day
1 to less than 3 times per day
Sometimes, but less than once per day
35. Do you regularly transmit, via e-mail, Internet, phone or fax, blood pressure readings to a health care provider for feedback?  Yes

Medication Use									
Are you currently taking any prescrip	□ yes	□ no							
Please list any prescription medications that you are taking:									
Medication Name	Dose	Times per Day	Is this me pressure?		Have you taken this medication regularly for at least 1 month?				
1.			□ yes	□no	☐ not sure	□ yes	□ no		
2.			□ yes	□no	☐ not sure	□ yes	□ no		
3.			□ yes	□no	☐ not sure	□ yes	□ no		
4.			□ yes	□no	☐ not sure	□ yes	□no		
5.			□ yes	□ yes	□no				
6.			☐ yes ☐ no ☐ not sure ☐ yes ☐ no						
7.			☐ yes ☐ no ☐ not sure ☐ yes ☐ no						
8.			☐ yes ☐ no ☐ not sure ☐ yes ☐ no						
9.			□ yes	□no	☐ not sure	□ yes	□ no		
10. □ yes □ no □ not sure □ yes □ no									

36. In order for blood pressure medication to work best, people should take it according to the doctor's instructions. For one reason or another, people can't or don't always take all of their pills as prescribed. We want to know how often you have missed your blood pressure medication. Please rate your agreement with the following statements.

On how many days over the past 7 days did you miss at least one dose of your blood pressure medication?

## Over the past 7 days....

I took all dos	ses of my blood pressure medication.
Never	
Rarely	
Sometir	mes
Often	
Always	
I missed or s	kipped at least one dose of my blood pressure medication.
Never	
 Rarely	
Sometii	mes
Often	
Always	
I was not ab	le to take all of my blood pressure medication.
Never	γ μ μ μ
 Rarely	
Sometii	
Often	
Always	
37. Have you	smoked at least 100 cigarettes in your entire life?
NOTE: 5 paci	ks = 100 cigarettes
Yes	
No	
Don't k	(now/Not sure

Food Allergies

 
Do you currently have any food allergies, food intolerances or do not eat certain foods?
 
Yes
 
No
 

 
2. Which foods? (Select all that apply to you)
 
 Milk or dairy
 
 Meat
 
 Eggs
 
 Fish or shellfish
 
 Nuts or seeds
 
 Wheat, gluten, corn or other grains
 
 Fruits or vegetables
 
 Beans or legumes
 
 Other foods**
 

3. If "Other foods" selected: What other food types?
4. Are you vegetarian? Yes No
5. Are you vegan?Yes No
Nutrition Self-Efficacy Scale

How certain are you that you could overcome the following barriers? Please respond from 0-100 where 0 is not at				
certain and 100 is completely certain.				
I can manage to stick to a dietary pattern that is rich in fruits and vegetables, legumes, beans, nuts, low-fat	0-100			
dairy, and lean protein foods	 			
even if I need a long time to develop the necessary routines.				
even if I have to try several times until it works.				
even if I have to rethink my entire way of nutrition	1			
even if I do not receive a great deal of support from others when making my first attempts	1			
even if I have to make a detailed plan				

For the next set of questions, please tell us how much you agree with the following statements about your eating habits.

Intuitive Eating Scale- 2 (IES-2)					
	Strongly disagree	Disagree	Neutral	Agree	Strongly agree
1. I try to avoid certain foods high in fat, carbohydrates or calories.					
2. I find myself eating when I'm feeling emotional (e.g. anxious, depressed, sad), even when I'm not physically hungry.					
3. If I'm craving certain foods, I allow myself to have it.					
4. I get mad at myself for eating something unhealthy.					
	Strongly disagree	Disagree	Neutral	Agree	Strongly agree
5. I find myself eating when I am lonely, even when I'm not physically hungry.					
6. I trust my body to tell me when to eat.					
7. I trust my body to tell me what to eat.					

8. I trust my body to tell me how much to eat.			
9. I have forbidden foods that I don't allow myself to eat.			
10. I use food to help me soothe my negative emotions.			
11. I find myself eating when I am stressed out, even when I'm not physically hungry.			
12. I am able to cope with my negative emotions (e.g. anxiety, sadness) without turning to food for comfort.			
13. When I am bored, I do NOT eat just for something to do.			
14. When I am lonely, I do NOT turn to food for comfort.			
15. I find other ways to cope with stress and anxiety than by eating.			
16. I allow myself to eat what food I desire at the moment.			
17. I do NOT follow eating rules or diet plans that dictate what, when, and/or how much to eat.			
18. Most of the time, I desire to eat nutritious foods.			
19. I mostly eat foods that make my body perform efficiently (well).			
20. I mostly eat foods that give my body energy and stamina.			
21. I rely on my hunger signals to tell me when to eat.			
22. I rely on my fullness (satiety) signals to tell me when to stop eating.			
23. I trust my body to tell me when to stop eating.			

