#### RCT:

We will randomize 300 men and women with a:

- normal blood pressure (systolic BP of <120 mmHg or diastolic BP: <80 mmHg with diagnosis of hypertension) and/or taking blood pressure medications
- systolic BP of 120-159 mmHg or diastolic BP: 80-99mmHg whether or not they are taking medications
- If the BP is above 140 mmHg for systolic or 90mmHg for diastolic and not taking medications, we will refer them to their physician for follow-up.
- If the BP is ineligible (160+ mmHg systolic and/or 100+ mmHg diastolic) and is not taking medications, but states that they plan to start taking BP-lowering medications (per their PCP's recommendation/prescription) within the study recruitment period, they can be offered to reach out the study team via phone/email when their BP has stabilized. The same protocols will apply (confirming BP for eligibility) at the visit. If they are still ineligible due to high BP at that point, no other follow-up will occur and they will not be randomized.

Additional inclusion criteria: Aged  $\geq 18$  years; BMI  $\geq 18.5$  kg/m; has a smartphone with a data plan 2 and an email address; willing to receive daily text messages; willing and able to participate in 6 videoconferencing research visits over the 12 month period; speaks English as primary language; currently lives in the United States.

Additional exclusion criteria: not willing to update phone/device operating system; participating in another related clinical trial; cardiovascular disease event (e.g. stroke, myocardial infarction) in prior 6 months; active malignancy; recent psychiatric institutionalization; pregnancy—current or planned during the study period; documented dementia, lives in the same household as another participant already enrolled in Nourish (due to concerns about contamination if randomized to different arms), bariatric surgery in the last 12 months; currently on kidney dialysis; was told by healthcare provider to not eat a high-potassium diet; and/or investigator-discretion.

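### As printed, the screener turns away anyone who has ever had a stroke, while the trial's exclusion criteria bar a stroke only in the prior 6 months

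*Combined protocol and SAP*

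**What the plan says.** Three places in the combined protocol and SAP bear on this.

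- **Subject Selection, RCT (additional exclusion criteria).** One exclusion is a "cardiovascular disease event (e.g. stroke, myocardial infarction) in prior 6 months". Stroke and myocardial infarction are named together under one window. No lifetime stroke exclusion is listed. The exclusion criteria for the formative phase use the same 6-month window.
- **Screening Survey, items 10 to 11a.** For myocardial infarction, item 10 asks the lifetime question and branches, and the exclusion sits on "10a. If yes, was it in the last 6 months". For stroke, the lifetime item reads "11. Have you ever been told by a doctor or other health professional or a stroke, also called an ischemic attack". Its exclusion column says "Exclude if yes", and its response-option and skip-logic cells are empty. The follow-up, "11a. If yes, was it in the last 6 months", has Yes/No options but an empty exclusion cell.
- **Screening Survey, scoring instruction below the table.** Staff are to "score the questions such that they are excluded if they answer any question as indicated by the last column in the table above".

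**The concern.** The scoring instruction makes the position of each rule operative: whatever stands in the last column decides who is turned away. With the stroke rule on the lifetime item, the screener applies a broader exclusion than the trial's stated criteria, and the 6-month question has no influence on the result.

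What is at stake is the match between the enrolled population and the one described. Adults with a remote stroke fall within the stated criteria, and the trial is meant to inform wide dissemination to adults with high blood pressure. Under the printed table they would be screened out automatically, while those with a remote myocardial infarction, treated identically in the criteria, would go forward. A report that quoted the protocol's criteria would then misdescribe who could enter.

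**Working it through.** No sample-size or power figure is involved, so the check sets the rules side by side.

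**Step 1. Apply each rule to the three possible stroke histories.** The second column uses the RCT exclusion criterion. The third scores the screener by its last column as printed. The fourth supposes that item 11 is not enforced because it prints no response options, which leaves only item 11a.

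| Stroke history | Exclusion criteria | Screener, item 11 enforced | Screener, item 11 not enforced |
|---|---|---|---|
| Never | not excluded | not excluded | not excluded |
| More than 6 months ago | not excluded | **excluded** | not excluded |
| Within 6 months | excluded | excluded | **not excluded** |

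Each version of the screener disagrees with the criteria for exactly one history (in bold). Scored as instructed, the error is over-exclusion of remote stroke. If item 11 is not enforced, the error is admission of recent stroke. Neither version reproduces the stated criterion.

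**Step 2. Compare with the other two-part items.**

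| Items | Topic | Branching on first item | Where the exclusion sits |
|---|---|---|---|
| 10 / 10a | Myocardial infarction | yes | follow-up (6 months) |
| 11 / 11a | Stroke | none printed | **lifetime item** |
| 12 / 12a | Cancer | yes | follow-up (remission) |
| 16 / 16a | Psychiatric hospitalisation | yes | follow-up (6 months) |

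The stroke pair is the only one of the four that breaks the pattern. The closest parallel outside cardiovascular history, "16a. If yes, was it in the last 6-months", carries its rule on the 6-month item. Item 11 also has words missing from its question.

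**Step 3. Look for a later step that would correct it.** The baseline survey and the measures table contain no stroke-history item. Visit 1 covers orientation and dietary tracking. Visit 2 covers blood pressure and medications. The computable phenotype for MyChart recruitment does not mention stroke. People scored as ineligible are shown a closing page. In the documents available, nothing after the screener restores a wrongly rejected person or catches a wrongly admitted one.

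**Step 4. Size.** The number affected would be the number screened, times the share with any stroke, times the share of those strokes more than 6 months old. The documents give none of the three, so no count is offered.

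**The case against.** The strongest reply is that this may be a fault of table layout or extraction. Item 11's row is visibly incomplete, and elsewhere in the table a rule does not always sit beside every item it governs: the rule for items 2a to 2d is printed on row 2a, and the BMI rule runs across items 18 and 19. An exclusion cell spanning 11 and 11a could print as it does here. Intent also looks clear, because a 6-month follow-up makes little sense if any stroke already excludes.

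Part of this stands. A displaced cell cannot be ruled out, and the documents show the specification, not the REDCap build. Checking the row must therefore come first. But the comparison rows are not quite alike: the rule for 2a to 2d names the items it covers, and the BMI text visibly continues from one row to the next, whereas the entry on item 11 is complete in itself. Clear intent does not remove the conflict either, because the scoring instruction follows the column and not the intent.

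A second reply is that the criteria allow exclusion at the investigator's discretion. That does not cover a fixed rule scored on every respondent's screener answers.

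A reader might also infer that a calculable share of eligible candidates is being lost. The documents do not support that. Any percentage would have to come from outside them.

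**Conclusion.** The point holds as an internal contradiction in an operative eligibility rule. As printed and scored, the screener excludes everyone with a stroke more than 6 months ago, a group that the exclusion criteria do not exclude. If item 11 is not enforced, a recent stroke passes instead.

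The conclusion rests on two assumptions: that the table was reproduced with its cells in the right columns, and that the REDCap screener was programmed from it. Both can be checked quickly.

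The consequence is confined to who enters and to how far the results generalise. Its size is unknown. A reader might infer damage to the trial's power or to its internal validity, but the documents give no ground for either: the target of 300 counts randomised participants, and the screener acts before randomisation and identically for both arms. Nor do the documents show that the enrolled sample did differ from the stated one, only that the printed rule would make it differ. The point should be resolved because the contradiction is plain and removing it costs little.

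**What to change.** 1. Check items 11 and 11a against the source table and the programmed REDCap logic, to establish which stroke rule is actually applied.
2. Reconcile the Screening Survey with the RCT exclusion criteria so that both state the same stroke window. If the criteria stand as written, this means placing the exclusion on item 11a, giving item 11 Yes/No options and skip logic parallel to item 10, and repairing its wording. If a lifetime stroke exclusion was intended, the exclusion criteria need to say so and item 11a serves no purpose.
3. If screening has already run under the printed rule, record the rule applied and its dates, and describe it when reporting eligibility.

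Under the criteria as they stand, the cost is one branching edit and one line of wording. The small downside of a change during recruitment is that early and late entrants may have been screened differently, which is why step 3 matters.
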